#### 8.4.2 SAE reporting

To ensure patient safety, every SAE, regardless of causality, occurring after the patient has provided informed consent and until 30 days after the last planned study assessment, must be reported to [REDACTED] within 24 hours of learning of its occurrence as described below. Any SAEs experienced after this period should only be reported to [REDACTED] if the Investigator suspects a causal relationship to study treatment.

Note: SAEs reported by patients deemed to be screen failures must be reported to [REDACTED] as outlined here with appropriate information also captured in the eCRFs.

All follow-up information for the SAE including information on complications, progression of the initial SAE and recurrent episodes must be reported as follow-up to the original episode within 24 hours of the Investigator receiving the follow-up information. An SAE occurring at a different time interval or otherwise considered completely unrelated to a previously reported one must be reported separately as a new event.

Follow-up information provided must describe whether the event has resolved or continues, if and how it was treated and whether the patient continued or withdrew from study participation. Each re-occurrence, complication, or progression of the original event must be reported as a follow-up to that event regardless of when it occurs.

If the SAE is not previously documented in the IB (new occurrence) and is thought to be related to the study treatment a [REDACTED] associate may urgently require further information from the Investigator for Health Authority reporting. [REDACTED] may need to issue an Investigator Notification (IN) to inform all investigators involved in any study with the same study treatment that this SAE has been reported. Suspected Unexpected Serious Adverse Reactions (SUSARs) will be collected and reported to the competent authorities and relevant ECs in accordance with EU Guidance 2011/C 172/01 or as per national regulatory requirements in participating countries.

Clinical endpoints described in [Section 5.4](#), such as bleeding events, ischemic stroke, hemorrhagic stroke, TIA, non-CNS systemic embolic events, venous thromboembolic events or myocardial infarction, that also meet SAE criteria will be collected as part of the endpoint

eCRF. These protocol-specific SAEs will not be reported on an individual basis in an expedited manner and instead will be adjudicated by an independent CEC. Fatal events will be reported regardless of adjudication on an aggregate basis to health authorities as required by local regulations. Other SAEs will be evaluated on a case-by-case basis to determine whether there is reasonable possibility that the study drug caused the event. If the event is considered by the sponsor or designee to meet the criteria for expedited reporting, the event will be reported in an expedited manner. Study endpoints and safety data will be regularly reviewed by an independent DMC in an unblinded manner to ensure prompt identification of any clinically concerning safety issues.

The investigator still has the responsibility to report all SAEs to the sponsor as described above. Follow the detailed instructions regarding the submission process for reporting SAEs to [REDACTED]. Note: SAEs must be reported to [REDACTED] within 24 hours of the Investigator learning of its occurrence/receiving follow-up information.

### **8.5 Reporting Medication errors including misuse/abuse**

Medication errors are unintentional errors in the prescribing, dispensing, administration or monitoring of a medicine while under the control of a healthcare professional, patient/subject, or consumer (EMA definition).

Misuse refers to situations where the medicinal product is intentionally and inappropriately used not in accordance with the protocol.

Abuse corresponds to the persistent or sporadic, intentional excessive use of a medicinal product, which is accompanied by harmful physical or psychological effects.

All study treatment errors and uses outside of what is foreseen in the protocol will be collected in the Dose Administration Record eCRF. Study treatment errors are only to be reported to [REDACTED] department if the treatment error is associated with an SAE.

All instances of misuse or abuse must be documented in the AE eCRF irrespective of the misuse/abuse being associated with an AE/SAE. In addition, all instances of misuse or abuse must be reported to the [REDACTED] department. As such, instances of misuse or abuse are also to be reported using the SAE form/eCRF. [Table 8-1](#) summarizes the reporting requirements.

**Table 8-1 Summary of Reporting Requirements for Medication Errors**

Treatment error type	Document in Dose Administration eCRF	Document in AE eCRF	Complete SAE form/eCRF
Unintentional study treatment error	Yes	Only if associated with an AE	Only if associated with an SAE
Misuse/Abuse	Yes	Yes	Yes, even if not associated with a SAE

For more information on AE and SAE definition and reporting requirements, please see [Section 8.1](#) and [Section 8.4](#), respectively.

### **8.6 Pregnancy reporting**

Reproductive toxicity and teratogenicity data are not available for this antibody at this time; therefore, no guidelines on therapeutic recommendations in case of pregnancy are available.

This study enrolls women who are either of non-child-bearing potential or who have agreed to highly effective contraception as outlined in the eligibility criteria; thus pregnancy is not an expected outcome for any female study participant. However, in the case that a pregnancy in a female study participant should occur please follow the below reporting guidelines. The appropriate clinical follow-up for this patient and for the fetus is at the discretion of the Investigator.

To ensure patient safety, each pregnancy occurring after signing the informed consent must be reported to [REDACTED] within 24 hours of learning of its occurrence. The pregnancy should be followed up to determine outcome, including spontaneous or voluntary termination, details of the birth, and the presence or absence of any birth defects, congenital abnormalities, or maternal and/or newborn complications.

Pregnancy must be recorded on the Pharmacovigilance Pregnancy Form and reported by the Investigator to the [REDACTED] department. Pregnancy follow-up should be recorded on the same form and should include an assessment of the possible relationship to the study treatment.

Any SAE experienced during the pregnancy and unrelated to the pregnancy must be reported on a SAE form.

If the Investigator becomes aware of a pregnancy occurring in the partner of a subject participating in the study, the pregnancy should be reported to [REDACTED] within 24 hours of becoming aware, using Pregnancy Report Form. Information regarding the pregnant partner must only be submitted after obtaining written consent from the pregnant partner. The pregnancy should be followed up to determine outcome, including spontaneous or voluntary termination, details of the birth, and the presence or absence of any birth defects, congenital abnormalities, or maternal and/or newborn complications.

All assessments that are considered as a risk during pregnancy must not be performed, such as venography. The patient may continue all other protocol assessments.

## 9 Data review and database management

### 9.1 Site monitoring

Before study initiation, at a (remote or in-person) site initiation visit or at an investigator's meeting, the Sponsor or Sponsor representative will review the protocol and eCRFs with the Investigator(s) and their staff. During the study [REDACTED] employs several methods of ensuring protocol and GCP compliance and the quality/integrity of the sites' data. The monitor will visit the site to check the completeness of patient records, the accuracy of entries on the eCRFs, the adherence to the protocol and to GCP, the progress of enrollment, and ensure that study drug is being stored, dispensed, and accounted for according to specifications. Key study personnel must be available to assist the monitor during these visits.

The Investigator must maintain source documents for each patient in the study, consisting of case and visit notes (hospital or clinic medical records) containing demographic and medical information, laboratory data, electrocardiograms, and the results of any other tests or assessments. All information on eCRFs must be traceable to these source documents in the patient's file. The Investigator must also keep the original informed consent form signed by the patient (a signed copy is given to the patient).

The Investigator must give the monitor access to all relevant source documents to confirm their consistency with the eCRF entries. [REDACTED] monitoring standards require full verification for the presence of informed consent, adherence to the eligibility criteria, documentation of SAEs,

and the recording of data that will be used for all primary and safety variables. Additional checks of the consistency of the source data with the eCRFs are performed according to the study-specific monitoring plan. No information in source documents about the identity of the patients will be disclosed.

## 9.2 Data collection

Designated investigator staff will enter the data required by the protocol into the Electronic Case Report Forms using fully validated software that conforms to 21 CFR Part 11 requirements. Designated investigator site staff will not be given access to the electronic data capture (EDC) system until they have been trained. Automatic validation programs check for data discrepancies and, by generating appropriate error messages, allow the data to be confirmed or corrected before transfer of the data to the contract research organization (CRO) working on behalf of Anthos Therapeutics. The Investigator must certify that the data entered into the Electronic Case Report Forms (eCRFs) are complete and accurate. After database lock, the Investigator will receive copies of the patient data for archiving at the investigational site.

Data not requiring a separate written record are noted on the Assessment Schedule and can be recorded directly on the eCRFs. All other data captured for this study will have an external originating source (either written or electronic) with the eCRF not being considered as source.

All data should be recorded, handled, and stored in a way that allows its accurate reporting, interpretation and verification.

## 9.3 Database management and quality control

[REDACTED] will review the data entered into the eCRFs by investigational staff for completeness and accuracy and instruct the site personnel to make any required corrections or additions.

Queries are sent to the investigational site using an electronic data query. Designated investigator site staff is required to respond to the query and confirm or correct the data.

Concomitant medications entered into the database will be coded using the WHO Drug Reference List, which employs the Anatomical Therapeutic Chemical classification system. Medical history/current medical conditions and adverse events will be coded using the medical dictionary for regulatory activities (MedDRA) terminology.

Except for the extension period, laboratory samples will be processed centrally, and the results will be sent electronically to [REDACTED]. During the extension period, safety laboratories will be performed locally.

At the conclusion of the study, the occurrence of any emergency code breaks will be determined after return of all code break reports and unused drug supplies to [REDACTED].

The occurrence of any protocol deviations will be determined. After these actions have been completed and the database has been declared to be complete and accurate, it will be locked, and the treatment codes will be made available for data analysis. Any changes to the database after that time can only be made by joint written agreement between the Anthos Therapeutics Head of Regulatory and the Chief Medical Officer.

## 10 Data analysis

A general description of the statistical methods to be used to analyze this study is outlined below. Further details can be found in the Statistical Analysis Plan (SAP).

### **10.1 Analysis sets**

- On-Treatment: will consist of all randomized patients who received at least one dose of study drug. Patients will be considered to be on-treatment if within 60 days of their last dose of study drug up to the EoT visit of the randomized treatment period.
- Intent-to-Treat (ITT): all patients randomized and dosed to be analyzed according to randomized treatment assignment. Events occurring from randomization through EoS of the randomized treatment period will be included in the analysis.
- Per Protocol: All randomized patients with a treatment compliance rate of at least 80% and do not have any major protocol violations as defined in the final SAP.
- On-Treatment Extension: will consist of all patients who received at least one dose of abelacimab in the extension period. Patients will be considered to be on-treatment if within 60 days of their last dose of study drug to the EoE visit of the extension period.

### **10.2 Patient demographics and other baseline characteristics**

Data for background and demographic variables will be listed by treatment group and patient. Summary statistics will be provided by treatment group.

Relevant medical history, current medical conditions, results of laboratory screens, drug tests and any other relevant information will be listed by treatment group and patient, and summary statistics will also be provided by treatment group.

### **10.3 Treatments**

Data for study drug administration and concomitant therapies will be listed by treatment group and patient.

### **10.4 Analysis of the primary variable(s)**

The primary analysis will compare each abelacimab regimen with rivaroxaban for the time to first occurrence of major or CRNM bleeding in the On-Treatment Analysis Set. For each treatment regimen, the event rate will be estimated with 95% confidence intervals (CIs). The time to first event will be analyzed using the Cox proportional hazards model including treatment and the following two stratification factors as covariates:

- Planned use of concomitant antiplatelet medication use (e.g., aspirin and/or P2Y12 inhibitor) for the duration of the trial
- CrCl (Cockcroft-Gault)  $\leq 50$  ml/min

The hazard ratios (HR) with 95% CIs will be reported for both doses of abelacimab vs. rivaroxaban. A significance level of  $\alpha=0.05$ , without adjustment for multiplicative testing, will be used. A sensitivity analysis will be performed in the ITT population.

The proportional hazards assumption in the Cox model will be assessed. A piecewise Cox model will be considered given evidence of non-proportional hazards.

### **10.5 Analysis of secondary variables**

Secondary endpoints will be analyzed following the testing procedure outlined in [Section 10.4](#).

### **10.5.1 Safety variables**

#### **10.5.1.1 Bleeding events**

All information obtained on bleeding events will be displayed by treatment group.

The number and percentage of patients with bleeding events will be tabulated by body system and preferred term with a breakdown by treatment. A patient with multiple bleeding events is only counted once towards the percentage of patients with bleeding events. Additional analysis by negative binomial may be carried out to compare bleeding event rates among treatment groups if sufficient bleeding events occur.

Bleeding events occurring during the extension period will be summarized as described in the SAP.

#### **10.5.1.2 Adverse events**

All information obtained on AEs will be displayed by treatment group and patient and will be summarized separately for the On-Treatment Analysis Set and the On-Treatment Extension Analysis Set.

The number and percentage of patients with AEs will be tabulated by body system and preferred term with a breakdown by treatment. A patient with multiple AEs within a body system is only counted once towards the total of this body system. Exposure-adjusted AE rates will also be summarized for both the On-Treatment Analysis Set and the On-Treatment Extension Analysis Set.

### **10.5.2 Vital signs**

All vital signs data will be listed by treatment group, patient, and visit/time and if ranges are available abnormalities (and relevant orthostatic changes) will be flagged. Summary statistics will be provided by treatment and visit/time.

### **10.5.3 ECG evaluations**

All ECG data will be listed by treatment group, patient and visit/time, abnormalities will be flagged. Summary statistics will be provided by treatment and visit/time.

### **10.5.4 Clinical laboratory evaluations**

All laboratory data will be listed by treatment group, patient, and visit/time and if normal ranges are available abnormalities will be flagged. Summary statistics will be provided by treatment and visit/time.

### **10.5.5 Other safety evaluations**

All injection site reaction data will be listed by treatment group, patient, and visit/time, and summarized by treatment group and visit/time as needed.

## **10.6 [REDACTED]**

[REDACTED]

[REDACTED]

[REDACTED]

### 10.6.1 Pharmacodynamics

All pharmacodynamic endpoints will be summarized by visit and treatment group including the ratio to baseline for each treatment along with their associated confidence intervals.

## 10.6.2 Pharmacokinetics

Plasma total abelacimab concentration data will be listed by dose, patient, and visit/sampling time point. Descriptive summary statistics will be provided by dose and visit/sampling time point, including the frequency (n, %) of concentrations below the LLOQ and reported as zero.

### 10.6.3 Pharmacokinetic / pharmacodynamic interactions

Graphical depictions of the relationship between plasma abelacimab concentrations and/or PK parameters and PD variables (for example: free FXI and aPTT) may be presented for the clinical study report.

The relationship between individual PK profiles or derived PK parameters and various efficacy/PD measurements or derived variables (for example: free FXI and aPTT) will be explored as appropriate. Additionally, the effect of relevant baseline characteristics (age, gender, body weight, baseline factor XI levels, baseline aPTT, etc.) on PK parameters and PD responses will be assessed as needed using a model-based approach that incorporates data from other studies with abelacimab. If available, these results may be summarized in the clinical study report; however, a separate analysis plan and final report for this analysis will be issued.

#### 10.6.4 Immunogenicity

All immunogenicity results will be listed by treatment group, patient, and visit/time.

### 10.6.5 Exploratory biomarkers

The primary endpoint is the composite

Assuming a HR of 0.69 for each dose of abelcimab compared with rivaroxaban, at least 166

events will provide at least 80% power for each abelacimab arm vs. rivaroxaban with a 2-sided alpha of 0.05. Given an expected 15% per year event rate in the rivaroxaban arm, a 10% annual dropout rate (death, withdrawal of consent, lost-to-follow-up), approximately 1,200 patients should provide the requisite number of events over a total trial duration of 27 months. We will

follow the event rates with the possibility of extending enrollment phase to preserve the planned duration of the trial.

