Statistical considerations	
Assuming a hazard ratio (HR) of 0.60 for each dose of abelacimab compared with rivaroxaban, at least 166 primary outcome events will provide at least 80% power for each abelacimab arm vs. rivaroxaban with a 2-sided alpha of 0.05. Approximately 1,200 patients should provide the requisite number of events over an estimated trial duration of 27 months.
 
The primary analysis will compare each abelacimab regimen with rivaroxaban for the time to first occurrence of major or CRNM bleeding in the On-Treatment Analysis Set. For each treatment regimen, the event rate will be estimated with 95% confidence intervals (CIs). The time to first event will be analyzed using the Cox proportional hazards model including treatment and the following two stratification factors as covariates:
 

1. Planned use of concomitant antiplatelet medication use (i.e., aspirin and/or P2Y12 inhibitor) for the duration of the trial

2. CrCl (Cockcroft-Gault) <math>\leq</math> 50 ml/min

Key words	Randomized, prospective, blinded endpoint evaluation, abelacimab, MAA868, rivaroxaban, atrial fibrillation

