## 6.2 Treatment assignment and randomization

Patients will be randomized on Day 1 to one of the following treatment arms in a 1:1:1 ratio:

- Abelacimab (MAA868) 90 mg s.c. monthly
- Abelacimab (MAA868) 150 mg s.c. monthly
- Rivaroxaban 20 mg p.o. once per day with evening meal

[Note: Patients with a CrCl  $\leq$  50 ml/min by the Cockcroft-Gault equation will have a dose adaptation to rivaroxaban 15 mg p.o. daily.]

Randomization into treatment groups will be stratified by the use of concomitant antiplatelet use at baseline (yes/no) and renal function (CrCl  $\leq$  50 ml/min or CrCl  $>$  50 ml/min). Patients randomized to the rivaroxaban arm may be dose adjusted between the 15 mg dose and 20 mg doses depending on CrCl values.

Once a subject is stratified and randomized, the subject will stay in that starting stratum, randomized treatment group, and treatment regimen for analyses purposes even if their dose is subsequently adjusted.

Once Investigators have ascertained that the patient is eligible for the study, they will contact the Interactive Web or Voice Response System (IxRS) before the first administration of study drug. The IxRS will require the following information in order to randomize a patient to the correct stratification: year of birth, CrCl (Cockcroft-Gault) and whether the patient takes antiplatelet medications (i.e., aspirin and/or a P2Y12 inhibitor) as a concomitant medication. The IxRS will allocate the treatment group assignment for the patient.

Emergency unblinding will be done through the IxRS system. The treatment code should not be broken except in medical emergencies when the appropriate management of the patient requires knowledge of the treatment assignment. The decision of whether or not to unblind lies with the investigator and it is the sole responsibility of the investigator to determine the need for immediate unblinding. However, if time and circumstances permit, the Investigator is encouraged to contact the [REDACTED]  
[REDACTED]  
[REDACTED]

The specifications for generation of the randomization schedule will be prepared by the study biostatistician and the contract research organization (CRO) in charge of the IxRS. An independent biostatistician, not otherwise part of the clinical study execution team, will generate the randomization schedule. The randomization numbers will be generated to ensure that treatment assignment is unbiased.

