### 2.2.3. Exploratory Objectives

### 2.3. Sample Size and Power

The primary endpoint is the composite of major or CNRM bleeding. The study is event driven. At the start of trial it was assumed a HR of 0.60 for each dose of abelacimab compared with rivaroxaban, thereby, a total of at least 166 events would provide at least 80% power for each abelacimab arm vs. rivaroxaban with a 2-sided alpha of 0.05. Given an expected 15% per year event rate in the rivaroxaban arm, a 10% annual dropout rate (death, withdrawal of consent,

lost-to-follow-up), approximately 1,200 patients would provide the requisite number of events over an approximate total trial duration of 27 months.

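### Protocol Section 10.7 ties 166 events and 80% power to HR 0.69; the synopsis and SAP use 0.60, and at 0.69 the power is about 52%

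*Protocol*

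**What the plan says.** Three places state the planning assumption.

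- Protocol Section 10.7, Sample size calculation (in the public copy the text follows the 10.6.5 heading): "Assuming a HR of 0.69 for each dose of abelcimab compared with rivaroxaban, at least 166", continuing "events will provide at least 80% power for each abelacimab arm vs. rivaroxaban with a 2-sided alpha of 0.05".
- Protocol synopsis, Statistical considerations: "Assuming a hazard ratio (HR) of 0.60 for each dose of abelacimab compared with rivaroxaban, at least 166 primary outcome events", again for at least 80% power per abelacimab arm at two-sided 0.05.
- SAP Section 2.3: "At the start of trial it was assumed a HR of 0.60 for each dose of abelacimab compared with rivaroxaban", and "a total of at least 166 events would provide at least 80% power for each abelacimab arm vs. rivaroxaban".

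Section 10.7 and SAP 2.3 also share a 15% annual event rate on rivaroxaban, 10% annual dropout, about 1,200 patients and about 27 months. Only the hazard ratio differs. No text explains 0.69, and SAP Section 7 reports no change from the analysis planned in the protocol.

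**The concern.** One event count cannot give 80% power at both 0.60 and 0.69 under the same alpha and allocation. One of the two statements must be wrong, and the outlier is in the protocol's own sample size section.

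The trial is event-driven, so the event target and the effect it can detect are its central design statement. Someone relying on Section 10.7 would believe that each comparison has 80% power for a 31% reduction in major or CRNM bleeding. The 166 events give that power for a 40% reduction. If the true hazard ratio were near 0.7, a non-significant result would be expected about half the time, yet Section 10.7 would present it as coming from an adequately powered test.

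**Working it through.** **Inputs**

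- Total events: 166. SAP 2.3 says this is a total.
- Alpha: 0.05 two-sided for each comparison, with no multiplicity adjustment (Protocol 10.4, SAP 6.6.1).
- Allocation: 1:1:1 (Protocol 6.2).
- Hazard ratio: 0.60 (synopsis, SAP 2.3) or 0.69 (Section 10.7), the same for both doses.

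**Formulas**

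Under equal allocation, expected events per arm are roughly proportional to the hazards 1 : HR : HR. The events in one abelacimab arm plus rivaroxaban are therefore

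d = 166 × (1 + HR) / (1 + 2 × HR).

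Schoenfeld's approximation for a 1:1 comparison gives

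power = Φ( √(d/4) × |ln HR| − 1.960 )

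and, for 80% power, required d = 4 × (1.960 + 0.842)² / (ln HR)² = 31.40 / (ln HR)².

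**The plan's figure at HR 0.60**

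- Expected split: 166/2.2 = 75.5 on rivaroxaban and 45.3 on each abelacimab arm.
- d = 166 × 1.60/2.20 = 120.7.
- Power = Φ(5.494 × 0.5108 − 1.960) = Φ(0.846) = 80.1%.
- Required d = 31.40/0.2609 = 120.3, so the required total is 120.3/0.7273 = 165.4, which rounds up to 166.

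The stated 166 events and 80% power are reproduced. This also confirms that 166 is the three-arm total.

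**The same calculation at HR 0.69**

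- d = 166 × 1.69/2.38 = 117.9.
- Power = Φ(5.428 × 0.3711 − 1.960) = Φ(0.054) = 52.2%.
- Required d = 31.40/0.1377 = 228.0, so the required total is 228.0/0.7101 = 321.1. Rounding the pairwise count up to 229 first gives 322.5, that is 323.
- Ratio to plan: 321.1/166 = 1.9.

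**Does another reading rescue 0.69?**

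| Reading of the 166 events | Power at HR 0.60 | Power at HR 0.69 |
|---|---|---|
| Three-arm total, Schoenfeld | 80.1% | 52.2% |
| Three-arm total, Freedman | 78.4% | 51.3% |
| Three-arm total, flat two-thirds per pair, Schoenfeld | 76.6% | 49.7% |
| Three-arm total, log-rank simulation (4,000 runs, stopped at 166 events) | 79.3% | 52.3% |
| Events per pair, Schoenfeld | 90.8% | 66.7% |
| Events per pair, one-sided 0.05, Schoenfeld | 95.0% | 77.2% |

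None reaches 80% at 0.69. The last row also contradicts the stated two-sided alpha. If 166 were events per pair, 80% power would correspond to a hazard ratio of 0.647, which is neither stated value.

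**The case against.** The strongest reply is that 0.69 may not be in the protocol at all. The paragraph is damaged in the public copy: the 10.7 heading is missing, the opening sentence breaks off, and the line with the figure also misspells the drug name. A misread digit cannot be excluded from the documents alone. That stands as a reason to look at the source page first. It does not remove the discrepancy, because the sentence carrying the number is legible and complete. A misspelling is as compatible with a drafting slip as with a reading error.

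A second reply is that nothing operational depends on the figure. The event target is 166 in all three places, the primary analysis does not use the planning hazard ratio, and the protocol sends readers to the SAP for detail. This is correct and limits the consequence to how the trial's sensitivity is described. But Section 10.7 is where a reader goes for the power statement, and that statement is false as it reads.

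A third reply is that 52% is the consequence of a figure nobody planned with. That is probably so. The 52% measures how wrong the sentence is; it is not evidence of an underpowered plan.

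**Conclusion.** The point holds. Section 10.7 states a planning hazard ratio that conflicts with the synopsis and the SAP and does not support its own power claim: about 52% instead of at least 80%, a shortfall of about 28 percentage points. Because 166 events reproduce almost exactly at 0.60, the error lies in the 0.69 and not in the event target.

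The 52% assumes that 166 is the total over three arms, that both doses share one hazard ratio, and proportional hazards. Reading 166 as events per pair raises the power at 0.69 to 66.7%, still well short of 80%. The one open matter is whether the source page itself prints 0.69.

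**What to change.** Check the source page of Protocol Section 10.7. If it reads 0.69, change it to 0.60 so that the protocol body, the synopsis and SAP 2.3 agree. If 0.69 was the intended planning value, keep it, restate the power for 166 events as about 52%, and reconcile the synopsis and SAP with it. If the protocol is no longer being amended, a clarifying note or a sentence in the clinical study report serves the same purpose.

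Correcting the slip costs one figure. The event target, patient number, analysis and conduct stay the same. If the source page already reads 0.60, nothing needs to change.
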